5.2 Discussion of Trial Design

This will be a single arm, open label, multicentre, 24-month Phase IV trial. Subjects with RMS will receive Mavenclad® 3.5 mg/kg body weight over two years, administered as 1 treatment course of 1.75 mg/kg per year. Each treatment course will consist of 2 treatment weeks, one at the beginning of the first month and one at the beginning of the second month of the respective year. There will be a 3-month window allowance for subjects for whom the second year course delays (5.4.1 and 5.5.1)

At *screening*, all subjects will have a pre-Baseline MRI scan as well as tuberculosis (TB; active and latent) and serology tests within the month leading up to the Baseline visit in order to support the diagnosis of highly active RMS and ensure compliance with inclusion and exclusion criteria.

Re-screening will be allowed once for those subjects who do not meet the inclusion/exclusion criteria within the above specified time limits. The Medical Monitor must promptly inform the Sponsor about requests and reasons for re-screening.

Baseline is defined as the day on which the first dose of Mavenclad® is administered. All Baseline assessment should take place before Mavenclad® administration.

Subjects will attend visits for assessments at Baseline, Month 6, 12, 14, 18, and 24. A time window of up to 3 months will be allowed for the visits following the second course (see also [Section 7](#)).

Subjects will attend visits for lymphocyte count as per mandatory monitoring at Screening, Baseline and at Months 2, 6, 12, 14, 18 and 24.

Subjects who discontinue Mavenclad® at any time during the trial will continue to participate in the scheduled visit for safety assessments and mandatory monitoring. In the event of early discontinuation from the trial, the subject should return for the Early Termination visit for final assessment.

Visit schedules for efficacy and safety assessments are detailed in [Appendix 1: Schedule of Assessments](#).

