6.2 Final Analysis

The final analysis will include all described analyses of this IAP except for the model of the TSQM v1.4 at Month 6 Visit (Section 0), which will only be done for the interim analysis. The TSQM v1.4 at Month 6 Visit will be included in a repeated model at the final analysis (Section 14.3.2).

The final analysis will be based on all data available in the database at the time of the final database lock.

7

Changes to the Planned Analyses in the Clinical Trial Protocol

Handling of data of subjects with a delayed 2nd treatment course:

The study protocol provides the following guidance how data of subjects with a delayed 2nd treatment course beyond 3 months should be handled in the statistical analyses.

Section 5.5.1: "Subjects with lymphopenia lower than the above-mentioned limit and/or occurrence of the above-mentioned infections, resulting in delay of scheduled second year treatment course beyond 3 months will be excluded from, tertiary or exploratory endpoint analysis."

Section 8.5.1: "Subjects for whom treatment is delayed by over 3 months may not have all assessment data captured and as such, these observations will be treated as missing."

As the data of the 1st treatment course are expected to provide valid efficacy information and the treatment delay of the 2nd year does not affect the 1st year course, it is decided that all data from the 1st treatment course should be included in all efficacy analyses while data from the 2nd treatment course will be excluded from all efficacy analyses for subjects with a delayed 2nd treatment course beyond three months.

For safety analyses, all data from both Treatment Courses will be used independently from the delayed start of Treatment Course 2. Section 9 defines the details of the data handling of subjects with a Delayed Treatment Course 2.

1-year interim analysis:

A 1-year IA was added during the course of the study without a corresponding protocol amendment.

COVID-19 pandemic:

Additional analyses to describe the potential impact of the COVID-19 pandemic added.

8 Protocol Deviations and Analysis Sets

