Treatment Period

The treatment period begins with the start of study medication on Study Day 1 and continues through to the completion of the treatment period at the Month 24 Visit (see protocol Section 7.1.3). Start of study medication is the date of first intake of study medication. Start of study medication in Year 2 is the date of first intake of study medication at or after the Month 12 Visit.

Treatment Period:

- Start = Start of study medication,
- End = Visit end date of Month 24 Visit or Early Termination (ET) Visit in case of early discontinuation, or the study discontinuation date, if the ET Visit was not performed.

Course 1 Treatment Period:

- Start = Start of study medication,
- End = Start of study medication at or after the Month 12 Visit -1 day or if the subject did not receive Treatment Course 2: Start of study medication of Treatment Course 1 + 457 days (which is obtained by 360 (12 months) + 90 (3 months) + 7 (visit window)), or date of the study discontinuation, if earlier.

Course 2 Treatment Period:

- Start = Start of study medication at or after the Month 12 Visit,
- End = End of Treatment Period.

Definition of Delayed Treatment Course 2

- The Treatment Course 2 will be defined as delayed, if the start of study medication is delayed by more than 3 months (=90 days) or did not start at all i.e.:
 - Start of Study Medication of Treatment Course 2 > Start of Study Medication of Treatment Course 1 + 457 days (which is obtained by 360 (12 months) + 90 (3 months) + 7 (visit window)), or
 - Treatment Course 2 never started (i.e. no study medication taken at or after the Month 12 Visit).

Data handling in case of a Delayed Treatment Course 2

For subjects with a Delayed Treatment Course 2, only data observed during the Course 1 Treatment Period will be analyzed in all efficacy analyses. Efficacy data after the Course 1 Treatment Period will be counted as missing in the statistical analyses and marked in the listings. In all efficacy analyses defined by Period, the subjects will be classified as if they discontinued at the end of the Course 1 Treatment Period. For subjects without a delay the whole Treatment Period will be analyzed.

For all other analyses (except efficacy) the data is not limited to the Course 1 Treatment Period for subjects with a Delayed Treatment Course 2.

Definition of start of COVID-19 pandemic

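### SAP Section 9 ends Course 1 follow-up at the study discontinuation date for subjects who never start Course 2, so an Early Termination score dated later, though within 457 days, is counted as missing

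*SAP*

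**What the plan says.** All the rules below are in SAP Section 9 unless stated otherwise.

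- **Treatment Period.** It runs to the last scheduled visit, "or Early Termination (ET) Visit in case of early discontinuation, or the study discontinuation date, if the ET Visit was not performed".
- **Subjects who did not receive Course 2.** Their Course 1 Treatment Period ends at the start of Course 1 medication + 457 days, "or date of the study discontinuation, if earlier". The ET Visit is not mentioned. The SAP explains the figure of 457 as one "which is obtained by 360 (12 months) + 90 (3 months) + 7 (visit window").
- **Delayed Treatment Course 2.** This class includes subjects for whom "Treatment Course 2 never started (i.e. no study medication taken at or after the Month 12 Visit").
- **Consequence for delayed subjects.** Only efficacy data from the Course 1 Treatment Period are analysed. "Efficacy data after the Course 1 Treatment Period will be counted as missing in the statistical analyses and marked in the listings".
- **ET mapping.** Unless specified otherwise, ET assessments are assigned to the nearest planned post-Baseline visit at which that assessment is missing.
- **SAP Section 7.** For subjects whose second course is delayed, "all data from the 1st treatment course should be included in all efficacy analyses". Section 7 leaves the details to Section 9.
- **Protocol 5.2 and 5.5.1.** "In the event of early discontinuation from the trial, the subject should return for the Early Termination visit for final assessment". Protocol 5.5.2 asks for the ET assessments immediately when withdrawal is for reasons other than withdrawn consent, but sets no day window. Protocol 7.1.10 makes the ET Visit the same as Month 24, so it includes MSQoL-54 and TSQM.

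**The concern.** Section 9 gives two ends of follow-up for the same early leaver. The Treatment Period definition treats the ET date and the discontinuation date as separate and gives the ET Visit priority: the discontinuation date applies only as a fallback, "or the study discontinuation date, if the ET Visit was not performed". The Course 1 definition has no such priority. Anyone who leaves before starting Course 2 is a delayed subject by definition, so the Course 1 definition decides which of that subject's efficacy scores are analysed.

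The protocol has the subject come back for the ET Visit after discontinuing, so an ET date later than the discontinuation date is foreseeable. MSQoL-54 is scheduled only at Baseline, Month 12 and Month 24. For someone who leaves before Month 12, the ET score is normally the only post-Baseline value, and without it the subject drops out of the change-from-Baseline model in SAP 14.1.1. Inclusion could then depend on whether the site enters the decision date or the ET Visit date as the discontinuation date.

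**Working it through.** **1. The plan's own figure.** 360 + 90 + 7 = 457 days, as SAP Section 9 states.

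**2. The date rules for a subject who never starts Course 2** (days after the start of study medication):

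- Course 1 end = min(457, discontinuation date)
- Treatment Period end = ET Visit end date if an ET Visit was done, otherwise the discontinuation date
- An ET efficacy score is analysed only if its date is on or before the Course 1 end.
- With the proposed wording, Course 1 end = min(457, Treatment Period end).

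The documents give no actual dates, so those below are assumed.

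| Discontinued | ET Visit | Course 1 end (now) | Treatment Period end | ET score now | ET score with fix |
|---|---|---|---|---|---|
| +200 | +200 | +200 | +200 | analysed | analysed |
| +200 | +201 | +200 | +201 | missing | analysed |
| +200 | +214 | +200 | +214 | missing | analysed |
| +330 | +344 | +330 | +344 | missing | analysed |
| +400 | +414 | +400 | +414 | missing | analysed |
| +450 | +464 | +450 | +464 | missing | missing (cap) |
| +600 | +614 | +457 | +614 | missing | missing (cap) |

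A gap of one day is enough to lose the score. For ET Visits after +457 the cap excludes the score under either wording.

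**3. Where the lost score would have gone.** The nominal visits are at 360 and 720 days. An ET score at +201 to +414 lies nearer to Month 12 (at +414: 54 days against 306), so it would fill Month 12 if that score is missing. If the Month 12 MSQoL-54 was done, Month 24 is the only unfilled visit, and the mapping rule would place the ET score at the primary time point. The figures in step 4 do not include this second route.

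**4. Illustrative size for the primary endpoint.** N = 445 is the planned number in the Protocol synopsis. Everything else is assumed: SD 20, exchangeable correlation 0.65 between visits, a further 5% random loss at Month 24, and leavers whose change is 10 points lower and who all lose the score mapped to Month 12. A simulation with 2,000 replicates compared the likelihood estimate of the Month 24 mean change with and without those scores:

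| Subjects affected | Shift in Month 24 mean change |
|---|---|
| 2% | +0.08 |
| 5% | +0.19 (0.24 SE) |
| 10% | +0.39 (0.46 SE) |

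The SE was 0.81 to 0.84; for example, 0.39/0.84 = 0.46.

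Hand check: the coefficient of Month 24 on Month 12 given Baseline is 0.65/(1 + 0.65) = 0.394. The shift is about 0.394 × fraction × 10, which gives 0.08, 0.20 and 0.39 and agrees with the simulation. The Month 12 mean at 5% moves by 0.05 × 10 = 0.5 points.

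**5. TSQM.** The final repeated model (SAP 14.3.2) is an efficacy analysis, so it is subject to the same rule. The Month 6 Global Satisfaction model is run only at the 6-month interim analysis (SAP 6.2 and 14.2). SAP 6.1.1 gives that analysis its own cut-off of start + 180 days when the Month 6 Visit is missing, and applies it expressly to subjects who discontinued earlier. Any loss there is limited to ET Visits up to that cut-off, and it is uncertain whether the delayed-course rule applies at all. At Month 6 nobody is due to have started Course 2, so a literal reading would class every subject as delayed.

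**The case against.** The strongest reply is that the loss is conditional. It needs an ET Visit dated after the recorded study discontinuation date. The SAP does not define that date, Protocol 5.5.2 asks for the ET assessments immediately, and a site may well enter the ET Visit date as the discontinuation date. Subjects who withdraw consent fall outside that instruction, which narrows the group further. This stands: a reader might infer that ET scores of Year 1 leavers are discarded as a rule, and the documents do not support that.

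Other stronger inferences also fail:

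- *That the ET mapping rule has no effect.* Subjects who start Course 2 on time and leave in Year 2 have their whole Treatment Period analysed, so their ET scores are mapped. So are those of never-starters whose ET Visit falls within 457 days and no later than the discontinuation date.
- *That the secondary endpoint is clearly biased.* The interim cut-off in SAP 6.1.1 stands between this clause and the Month 6 model.
- *That Section 7 is flatly contradicted.* Section 7 states an aim and hands the boundary to Section 9. The boundary as written works against the aim.

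The conflict inside Section 9 remains. The Treatment Period definition shows that its authors saw the two dates as different and preferred the ET Visit. Section 7 justifies excluding second-course data, and nothing in it argues for dropping an ET score taken during first-course follow-up.

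**Conclusion.** The point holds as an internal conflict in SAP Section 9. For a subject who never starts Course 2, an ET efficacy score dated after the recorded discontinuation date and no later than start + 457 days is counted as missing, although the ET mapping rule and the aim in Section 7 would have it analysed. For a subject who leaves before Month 12, this can decide entry into the primary model.

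The number affected cannot be computed from the documents and may be zero. Under the assumptions in step 4, with 5–10% of subjects affected, the Month 24 mean change rises by about 0.2–0.4 points on a 0–100 scale (0.24–0.46 SE). A reader might infer a favourable bias, but that direction follows only from assuming that leavers score lower. If the lost scores do not differ systematically given the modelled data, which is the missing-at-random assumption of SAP 14.1.1, there is no expected bias even when scores are lost. The study is single-arm and exploratory, so no confirmatory test is at stake. The rule should still be corrected, because it is wrong as written and could lead two programmers to different primary datasets.

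**What to change.** In SAP Section 9, change the end of the Course 1 Treatment Period for subjects who did not receive Course 2 to: *457 days after the start of Course 1 medication, or the end of the Treatment Period as already defined (ET Visit end date; discontinuation date where no ET Visit took place), whichever comes first.*

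ET assessments made within the 457 days are then analysed, and the two definitions and the mapping rule agree. ET Visits after the cap stay excluded, as now. The cost is one clause in the SAP and one line in the program that flags the period. No new data are needed.

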8.2 Definition of Analysis Sets and Subgroups

Enrolled Set (ES)

All subjects enrolled in the study, i.e. all subjects with a signed informed consent.

Intent-to-treat Set (ITT)

All subjects classified as eligible (i.e. medication assigned by iRT at the Baseline Visit).

Full Analysis Set (FAS)

All subjects from the ITT treated with at least one dose of study medication.

Treatment Completer Set – Year 1 (TCS-1)

All subjects from the FAS who completed the full Treatment Course of the first year (Treatment Course 1). Subjects will be classified as Treatment Completer for the first year, if they have a compliance greater than or equal to 100% for Treatment Course 1.

Treatment Completer Set – Year 2 (TCS-2)

All subjects from the FAS who completed the full Treatment Course of the first and the second year. Subjects will be classified as Treatment Completer for the second year, if they have a compliance greater than or equal to 100% for Treatment Course 1 and Treatment Course 2 and received the treatment without delay (see Section 9 for definition).

Safety Analysis Set (SAF)

All subjects treated with at least one dose of study medication.

Unless otherwise specified, all efficacy analyses will be performed on the FAS. The primary analysis will be repeated on the Treatment Completer Sets and on the ITT, if different, to evaluate

the sensitivity of the primary results to deviations of the planned treatment regimen. Further details are given in the respective sections. All safety analyses will be performed on the SAF.

Additional Subgroup Analysis Sets

Subgroup analyses will be performed on subgroups as defined below.

Previous treatment with Disease Modifying Drugs (DMDs):

- **DMD pre-treated:** Subjects will be categorized as DMD pre-treated if they have taken DMDs any time before start of study medication. Details of the definition of DMDs are specified in Appendix 1 (Section 18.1).
- **Pre-treatment naïve:** all subjects not classified as DMD pre-treated.

Unless otherwise indicated, all descriptive statistical analyses will be presented separately for pre-treatment naïve and DMD pre-treated subjects.

Month 12 MSQoL assessment after start of COVID-19 pandemic:

- **Yes:** Date of Month 12 MSQoL assessment (if missing, Month 12a Visit End Date) after start of COVID-19 pandemic (see Section 9 for definition).
- **No:** Otherwise.

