The start of COVID-19 pandemic will be defined by country as the earliest date of either the date of the first death from COVID-19 occurred in each country according to the published data by European Centre for Disease Prevention and Control on 26th June 2020 (<https://www.ecdc.europa.eu/en/publications-data/download-todays-data-geographic-distribution-covid-19-cases-worldwide>) or 11th March 2020 (when the WHO declared COVID-19 pandemic).

Visit timing with respect to COVID-19 pandemic

A visit is defined to be performed after the start of COVID-19 pandemic if the visit end date is greater than the start of COVID-19 pandemic date.

Conversion factors

The following conversion factors will be used to convert days into months or years for all observations except Visit related dates:

- 1 month = 30.4375 days,
- 1 year = 365.25 days.

Time window

- Day 1 is the day of start of study medication, the day before is Day -1 (no Day 0 is defined).
- Study day / Treatment day is defined relative to Day 1.

The visit schedule is defined as follows:

- 1 month = 30 days,
- 1 year = 360 days,

relative to the start date of the Baseline Visit for Treatment Course 1 and relative to the start date of the Month 12b Visit as defined in the eCRF (see also Section 15.3) for Treatment Course 2.

In each analysis, should assessment be delayed, subjects' assessment data will be treated as though it occurred at the time point specified (i.e. out of visit windows will be not excluded or adjusted for any analyses) and inferences will be conducted accordingly. Thus, further time windows will not be specified.

All observations from unscheduled Visits will be included only in the analyses of Visit independent summaries (e.g. counts of events, progressions or worst value during Treatment Period) unless for the last assessment available. In this case the missing ET visit will be imputed by the unscheduled visit.

If not specified otherwise, the assessments of the ET visit will be mapped to the nearest next planned post-baseline visit with a missing assessment before or after the ET visit of the individual assessment for all statistical analyses and descriptive summaries. As not all assessments of the ET

are performed at each visit, the different assessments of the ET can be assigned to different visits. If the duration (in days) between the ET visits and two missing planned visits are equal, then the assessment will be assigned to the later visit.

Handling of missing data

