14.1.1 Primary Objective: Analysis of the primary endpoints

The primary objective is to assess the HRQoL through the MSQoL-54 scale in highly active RMS subjects treated with Mavenclad® for 2 years (24 months).

The primary endpoints for the study are the changes in HRQoL assessed by MSQoL-54 physical health and mental health at 24 months post-Baseline assessment. Differences in MSQoL-54 scores between measurements at the Month 24 Visit and Baseline will be assessed using repeated mixed-effects linear regression, accounting for clinically relevant factors, within subject correlation and within pooled center correlation.

As the analysis set concerns repeated measurements for outcomes for each individual, it is likely that observations pertaining to each individual will be correlated. Furthermore, as this is a multi-center study, it is likely that clustering of individuals within study sites will produce an additional source of correlation. Mixed-effects regression, whereby a three-level hierarchical model is specified for observations within subjects within-pooled centers, will be used to account for within-subject and within-pooled center correlation (Gibbons et al., 2010).

The analysis will also adjust for factors deemed to be prognostic for the primary endpoint, as judged by clinical experts. These factors are the age and EDSS at Baseline, (see Section 9 for details).

The primary endpoints are the changes from Baseline to Month 24 Visit in Physical and Mental health composite of the MSQoL-54. They will be analyzed with a repeated mixed-effects linear model for change from Baseline that will take all planned intermediate measurements into account whereby a three-level (visits within subjects within centers) hierarchical model is specified for repeated MSQoL-54 Physical or Mental health composite scores.

$$Y = X\beta + \gamma + e, \text{ where}$$

Y represents change from baseline in MSQoL score,

X represents values of fixed effects including MSQoL score, age and EDSS at Baseline, and Visit (defined as a class variable),

β represents set of regression coefficients,

γ represents pooled center random effect,

e represents a random error, potentially correlated for different visits within a subject (nested within a center).

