The LS Means will be calculated with observed margin which reflects the distribution of age, ~~g~~ categories at Baseline and respective Baseline composite score of the FAS. An unstructured covariance matrix will be assumed for the model. If the model doesn't converge a variance components covariance structure will be used instead or the center effect will be specified as a fixed effect instead (same model as specified as a sensitivity analysis below).

The following hypotheses will be evaluated exploratively:

$$H_{01}: \Delta_{\text{Physical Health}} = 0 \text{ vs. } H_{11}: \Delta_{\text{Physical Health}} \neq 0$$

$$H_{02}: \Delta_{\text{Mental Health}} = 0 \text{ vs. } H_{12}: \Delta_{\text{Mental Health}} \neq 0,$$

where $\Delta = EY$ denotes the population mean change of the respective score.

The study is exploratory in nature. A control of the potential type-I-error inflation caused by multiple endpoints and multiple testing is not implemented.

Analysis (Analysis Set)	Derivation	Statistical Analysis Methods	Missing data handling
Primary endpoint: Changes in MSQoL-54 physical and mental health composite scores from Baseline to Month 24			
Primary (FAS)	Changes from Baseline in physical health composite (MSQoL-54) to the Month 12 Visit and Month 24 Visit	Repeated mixed-effects linear model with the following adjusting factors: 
• Baseline score,• Age (years),• EDSS (≤ 3, > 3),• Visit,• Within-pooled center correlations,• Within-subject correlation. Estimated Least Square Means (LS Means) and corresponding Standard Errors (SE) will be presented by Visit including 2-sided p-values and 95% CI that are not adjusted for multiple testing due to the exploratory nature of the study.	Missings at Baseline: Subjects with a missing MSQoL assessment at Baseline will not be included in the repeated mixed-effect linear model analysis. Missing covariate or stratification information will be imputed as specified in Section 9. Missing post-Baseline observations: Missing post-Baseline assessments will not be imputed. The repeated measurement model handles missing post-Baseline assessments under the assumption of missing at random. Missing Sexual function scores: See below.
Primary (FAS)	Changes from Baseline in mental health composite (MSQoL-54) to the Month 12 Visit and Month 24 Visit		

Handling of missing scores in sexual function:

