15.3 Clinical Laboratory Evaluation

Lymphocyte counts from local laboratory will be used for summary statistics and shift tables. They will be classified according to the NCI-CTCAE (latest version available). The classification will be derived only from the laboratory results at a given assessment, thus ignoring the underlying syndrome.

The Treatment Course 2 can be delayed because of Lymphocyte count below 800 cells/mm³ at the Month 12 Visit. In this case, the Lymphocyte count can be measured several times between the Month 12 Visit and the start of Treatment Course 2. Lymphocyte counts at or after the visit start date of the Month 12 Visit and before or at the start date of the Treatment Course 2 will be displayed as follows:

- The earliest Lymphocyte count will be assigned to the Month 12 Visit,
- The latest Lymphocyte will be assigned to the Month 12b Visit,
- All other Lymphocyte count will be assigned to unscheduled visits.

A Lymphocyte count can be assigned to the Month 12 Visit and Month 12b Visit, if just one count is available. If the Treatment Course 2 wasn't started, only the earliest Lymphocyte count will be assigned to the Month 12 Visit.

The worst on-study grade (i.e. on or after first study treatment administration) will be summarized considering only subjects with post Baseline laboratory samples: Laboratory tests by NCI-CTCAE grade (0, 1, 2, 3, 4, any).

Lymphocyte counts will be examined for trends using descriptive statistics (mean, SD, median, Q1, Q3, minimum, and maximum) of actual values and changes from Baseline to each scheduled Visit including Month 12b Visit over time. If for a particular visit a different local laboratory than normal laboratory was used (due to COVID-19 pandemic), values collected during that visit will not be included in the descriptive statistics.

Shift tables of Baseline versus endpoint (as well as the worst value at any post-Baseline Visit) will be presented. Abnormalities classified according to NCI-CTCAE toxicity grading (latest version available) will be described using the worst grade.

All Lymphocyte counts will be listed by subject for the SAF.

Positive results of the tuberculosis and serology tests that do not comply with the protocol will be listed.

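### Early-termination MSQoL-54 values are mapped to the nearest open visit with no distance limit, so values taken up to about a year early can count as Month 24 in the primary model

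*SAP*

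**What the plan says.** Protocol 7.3.1.1 schedules MSQoL-54 at Baseline, Month 12 and Month 24. Protocol 7.1.10 applies the Month 24 procedures, which include MSQoL-54, to subjects who leave the trial early.

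SAP Section 9 (Time window) has each ET assessment "mapped to the nearest next planned post-baseline visit with a missing assessment before or after the ET visit". This applies to all analyses unless specified otherwise, and ties go to the later visit. A last unscheduled assessment may stand in for a missing ET visit. The section adds that out-of-window data are neither excluded nor adjusted and that no further windows will be set.

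SAP 14.1.1 models change from Baseline with Visit as a categorical effect. On missing data it says: "Missing post-Baseline assessments will not be imputed". It relies on missing at random for those values.

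For a second course delayed beyond three months, SAP Section 7 says that "data from the 2nd treatment course will be excluded from all efficacy analyses for subjects with a delayed 2nd treatment course beyond three months"; the same sentence keeps all first-course data in all efficacy analyses. SAP Section 9 counts a course that never started as delayed and adds: "Efficacy data after the Course 1 Treatment Period will be counted as missing in the statistical analyses". For a never-starter, that period ends 457 days after the start of medication, or at study discontinuation if earlier.

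**The concern.** The primary endpoint is the change at 24 months, but the mapping rule looks only for the nearest empty slot. With two post-baseline slots, a subject who leaves shortly after Month 12 supplies a value labelled Month 24 that was measured about a year too soon. Because Visit is categorical, the model treats it like a value taken on schedule. The subject's Month 24 is then no longer handled as missing at random, and 14.1.1 does not tell the reader so.

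The rule also treats similar subjects differently. Take two subjects who have Month 12 data and never start Course 2. The one who leaves by day 457 can supply a Month 24 value. The one who stays and completes the real Month 24 questionnaire has that value set to missing.

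At stake is whether the Month 24 estimate describes 24 months. The trial has a single arm, so no comparator can offset mistimed values.

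**Working it through.** **Inputs.** Days are counted from the start of Course 1.
- SAP Section 9: 1 year = 360 days, so Month 12 = day 360. Month 24 = Month 12b + 360, which is day 720 if Course 2 starts on time.
- Mapping: nearest planned visit with that assessment missing; ties go to the later visit.
- Planned sample size: 445 (Protocol Synopsis).

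**The plan's own figure.** 360 + 90 + 7 = 457, which reproduces the end of the Course 1 Treatment Period when Course 2 is not received.

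**Month 12 observed, Course 2 on time.** Month 24 is the only open slot. Shift = 720 − exit day.
- Day 361: 359 days early. Day 540: 180 days. Day 719: 1 day.
- Possible exit days: 719 − 361 + 1 = 359.
- Reference distance: 7-day window + 90-day allowance = 97 days. The shift exceeds 97 on days 361-622, which is 262 days; 262/359 = 73%.
- If Month 12b is on day 367, 450 or 457, Month 24 is day 727, 810 or 817, and exits after Month 12b again give 1-359 days.

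**Course 2 never started, Month 12 observed.** ET values are retained up to day 457, provided the ET visit is not after the recorded discontinuation date. Retained exits fall on days 361-457 (97 days). With Month 24 taken as day 720 (assumed), the shift runs from 720 − 457 = 263 to 720 − 361 = 359 days.

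**Course 2 started after day 457.** The Course 1 Treatment Period ends the day before Course 2 starts, so a later ET value is already missing. These subjects are not affected.

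**Month 12 missing.** An exit before day 360 fills Month 12, 1-359 days early. A retained value from day 540 onward goes to Month 24, since the tie at day 540 goes to the later visit.

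**Possible counts (assumption).** Suppose 2-10% of 445 subjects leave after Month 12 with an ET value, uniformly over days 361-719.
- Mapped values: 8.9 to 44.5, about 9-45.
- More than 97 days early: × 262/359 = 6.5 to 32.5.
- On days 361-457, the only days that can give retained never-starter values: × 97/359 = 2.4 to 12.0, so at most about 2-12.

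**Scale of effect (assumption).** If 2-10% of Month 24 values are mapped and differ from the true Month 24 value by 2-10 points, the raw mean moves by 0.02 × 2 = 0.04 to 0.10 × 10 = 1.0 points, in an unknown direction.

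**The case against.** The rule is deliberate and disclosed. The protocol makes Final, Early Termination and Month 24 a single visit, and the SAP states the mapping for all analyses with a tie rule. The trial is exploratory without type-I-error control, and subjects who only stop the drug stay on scheduled visits. Composite scores and discontinued subjects are listed. Section 14.1.1 refers to a sensitivity analysis in text that is now redacted, and the mapping opens with an exception clause, so a check or an override may exist there. All of this stands. It argues for keeping the rule and for a modest remedy, but it does not tell the reader how much of the Month 24 estimate was measured near Month 24.

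A reader might infer more than the documents support:
- *That the mapping contradicts 14.1.1.* It does not. A mapped value is observed, so the statement about missing values does not cover it.
- *That SAP Section 7 already bars never-starter ET values from Month 24.* It does not. That section keeps all first-course data, and these values are first-course data.
- *That the lack of an explicit Month 24 date for never-starters leaves their mapping undefined.* It has no effect on MSQoL-54. With Month 12 observed, only Month 24 is open. With Month 12 missing, day 457 is 97 days from Month 12 and at least 263 from Month 24, so the value goes to Month 12.
- *That the repeat on the Year 2 completer set shows which exits remain.* That set requires "compliance greater than or equal to 100% for Treatment Course 1 and Treatment Course 2 and received the treatment without delay", so it removes never-starters and delayed subjects. But SAP Section 13 leaves treatment weeks after discontinuation out of compliance, so a subject who stops before the second week of Course 2 can still reach 100%. No firm exit-day count follows.

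**Conclusion.** The concern holds. As written, the rule lets MSQoL-54 values taken 1-359 days early enter the primary model as Month 24, and 73% of the possible exit days after Month 12 give a shift of more than 97 days. For never-starters every retained value after an observed Month 12 is 263-359 days early if Month 24 is day 720.

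The reach is limited to trial exits with an ET or substituted unscheduled value. It would be tempting to call the Month 24 result biased. The documents give no exit rate, no count of ET values and no MSQoL-54 trajectory, so neither the size nor the direction of any bias can be computed; the counts and point shifts above are illustrations. Nor can it be said that no check is planned, only that none is visible. The issue is worth fixing because the remedy is cheap. Confidence is medium because of the redaction.

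**What to change.** (a) Keep the mapping as the primary rule. Add a sensitivity analysis of the primary model that leaves missing both the mapped ET (or substituted unscheduled) values further than a pre-stated distance from the planned visit and all never-starter ET values mapped to Month 24. The distance could be 97 days, as an example only. If the redacted text already contains this analysis, it is not needed.

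(b) Report how many Month 12 and Month 24 values are mapped ET values and their shift in days, for example beside the MSQoL-54 completion status in SAP 10.1. Cross-reference the mapping rule in 14.1.1.

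If the sponsor prefers to bar never-starter ET values from Month 24 in the primary analysis, the SAP should state this as an explicit exception to Section 7, which includes all first-course data in all efficacy analyses.

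**Cost.** One model run, one table row and one cross-reference; the primary result does not change. The sensitivity run has fewer Month 24 values. Treating Month 24 as a simple mean over 445 and using the uniform-exit assumption, losing 6.5-32.5 values multiplies the SE by √(445/438.5) = 1.007 to √(445/412.5) = 1.039. Barring only never-starter values (at most 2.4-12.0) gives √(445/442.6) = 1.003 to √(445/433.0) = 1.014, or 0.3-1.4%. A 97-day limit would also leave exits before day 360 − 97 = 263 with no post-baseline value, so it is suggested for a sensitivity analysis only.
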